### **5.3. REPORTING/RECORDING OF AEs**

---

Throughout the course of the study, all efforts will be made by the Investigator to remain alert to possible AEs. The first concern will be the safety of the subject, and

---

for providing appropriate medical intervention. The period of observation for collection of AEs starts during the first intramuscular injection procedure (Day 0) until the 9 month follow-up visit. Any AE should be recorded on the appropriate CRF page(s).

---

#### **5.4. REPORTING / RECORDING OF SAEs**

---

##### **5.4.1. INVESTIGATOR'S RESPONSIBILITY**

---

SAEs will be recorded following the first study drug administration through the 9 month follow-up visit. Any SAE that occurs during this investigation, whether or not related to the study medication, must be reported immediately (within 72 hours) to the Sponsor and MedTech Consultants, Inc., the designated CRO.

Each SAE must be followed with appropriate medical management until resolved or assessed as chronic or stable regardless of whether or not, in the opinion of the Investigator, the event is thought to be related to the study medication.

The Investigator will be required to provide complete information concerning each SAE to the CRO and Sponsor within 5 calendar days of the event. This information must be recorded in the subject's medical record and then transcribed onto the SAE FAX Form. The completed SAE Form (including the Investigator's opinion of the relationship of the SAE to the study medication), copies of related results/reports, consultant report(s), and other relevant information will be faxed and/or mailed to the CRO.

In the event of an SAE leading to hospitalization, every effort will be made by the investigational site to obtain medical records, including a hospital discharge summary. In the event of a fatal AE, documentation of any available postmortem findings, including autopsy, will be provided to the Sponsor or their designee. In any event, the Investigator will provide a narrative summary of circumstances, events related to the death, and cause of death, if known. Any follow-up information obtained must be recorded on an SAE follow-up report form.

The Investigator must comply with the applicable local regulatory requirements related to the reporting of SAEs to regulatory authorities and the Institutional Review Board (IRB), and Institutional Biosafety Committee (IBC) if applicable. Upon receipt from the Sponsor of an initial or follow-up IND Safety Report or other safety information, the Investigator must promptly notify his or her IRB, and IBC (if applicable).

##### **5.4.2. SPONSOR'S RESPONSIBILITY**

---

All AEs and SAEs will be reported on an annual basis to FDA in accordance with the IND regulation (21 CFR Part 312). Per the 2010 FDA Guidance Document for Industry and Investigators — Safety Reporting Requirements for INDs and BA/BE Studies,” events categorized as possibly or probably related will be treated as

---

‘suspected adverse reactions.’ Events categorized as ‘definitely’ related will be treated as an ‘adverse reaction.’

All serious, unexpected adverse reactions and suspected adverse reactions will be reported to FDA and to all participating Investigators as an IND Safety Report within 15 calendar days of the event after the sponsor determines that the suspected adverse reaction qualifies for reporting (21 CFR §312.32). Any unexpected fatal or life-threatening AEs will be reported to the Agency within 7 calendar days after the sponsor’s initial receipt of the information.

The Sponsor will notify all participating Investigators of any new safety information that alters the current risk-benefit assessment of the study medication or that would be sufficient to consider changes in VM202 administration or in the overall conduct of the trial.

---

## 6. STATISTICAL METHODS

---

The objective of this Phase I/II study is to evaluate the safety of IM administration of VM202 in subjects with amyotrophic lateral sclerosis. Sample size estimations were not based on formal statistical hypotheses testing due to the exploratory nature of this Phase I/II study. Hypothesis testing will not be performed on any endpoint.

### 6.1. PATIENT CATEGORIZATION

---

**Screen Failure** - Any patient who was consented and entered into the screening process appropriately, but subsequently did not meet the entry criteria in order to be treated. Patients who fail screening will not be followed for safety or efficacy assessment, and no other study procedures will be performed.

**Evaluable Patient** - Any patient who received the study drug.

**Lost to follow-up** - A patient deemed to be lost to follow-up is any patient who received treatment, but who does not complete scheduled study visits to 9 months. This includes those patients who withdraw consent and refuse further study participation and all attempts to contact the patient are deemed unsuccessful.

---

### 6.2. STUDY ENDPOINTS

---

The primary study endpoint is to evaluate safety and tolerability of intramuscular injections of VM202 at different injection sites in subjects with ALS. Secondary endpoints include the assessment of the potential of VM202 to reduce neurodegeneration and muscle wasting as determined by the ALSFRS-R, muscle strength (MRC scale), muscle circumference measurements and dynamometry. FVC will also be tracked and trended.

---

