**STUDY ENDPOINTS**

The primary study endpoint is to evaluate safety and tolerability of intramuscular injections of VM202 at different injection sites in subjects with ALS. Secondary endpoints include the assessment of the neuroprotective potential of VM202.

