**SAFETY**

Adverse events (including serious adverse events, and adverse events leading to treatment discontinuation) throughout the 9 months follow-up will be described according to severity and to their relationship with the study drug and injection procedure. Descriptive statistics will be used to characterize safety parameters.

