## **3. INVESTIGATIONAL PLAN**

### **3.1. STUDY OBJECTIVES**

The objective of this Phase I/II study is to evaluate the safety and tolerability of IM administration of VM202 at different injection sites in subjects with ALS.

---

---

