#### **4.2.11. INJECTION SITE REACTION ASSESSMENT**

Local injection sites reactions will be assessed on Day 0 post injection, Day 7 pre and post injection, Day 14 pre and post injection, Day 21 pre and post injection, Day 30, and Day 60. Any adverse reaction should be reported as an AE.

---

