## 5.2. ASSESSMENT OF AEs

---

All AEs experienced by study subjects, regardless of severity, which occur between the first study drug administration and the 9 month follow-up visit of the study must be recorded on the AE form provided with the CRF. This will include the following information:

- Description of the AE
- Date of onset
- Duration
- Frequency
- Severity
- Seriousness (yes/no)

- 
- Treatment
  - Outcome
  - Relationship to study medication, injection procedure and/or underlying disease

All AEs and SAEs must be followed until resolution, or the condition stabilizes. The Investigator is responsible to ensure that follow-up includes any supplemental investigations as may be indicated to elucidate as completely as possible the nature and/or causality of the AE or SAE. This may include additional laboratory tests or investigations, histopathological examinations, or consultation with other health care professionals. The Sponsor or its designee may request that the Investigator perform or arrange for the conduct of supplemental measurements and/or evaluations.

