### **6.2.1. SAFETY**

Any patient who receives VM202 will be included in the safety analysis population. Adverse events, serious adverse events, and adverse events leading to treatment discontinuation will be summarized using descriptive statistics. Categorical variables will be summarized by the number and percentage of patients in each category. Continuous variables will be summarized using n, mean, SD, median, minimum, and maximum values. No statistical testing will be performed.

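### The primary endpoint can be read as asking for safety by injection site, but no by-site summary is planned and the protocol does not ensure that reaction location is recorded

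*Combined protocol and SAP*

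**What the plan says.** **Aim.** Section 6.2 gives the primary endpoint as to "evaluate safety and tolerability of intramuscular injections of VM202 at different injection sites in subjects with ALS". The synopsis has the same statement: "The primary study endpoint is to evaluate safety and tolerability of intramuscular injections of VM202 at different injection sites in subjects with ALS". Section 3.1 gives the objective as to "evaluate the safety and tolerability of IM administration of VM202 at different injection sites in subjects with ALS". The opening of section 6 restates the objective as to "evaluate the safety of IM administration of VM202 in subjects with amyotrophic lateral sclerosis", which drops both tolerability and the site wording. The title and study-design entries of the synopsis and the opening of section 3.2 also leave out the site wording.

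**Collection.** Section 4.2.11 gives the times of the injection-site assessment and adds: "Any adverse reaction should be reported as an AE". Section 5.2 says that AEs "must be recorded on the AE form provided with the CRF" and lists nine items: description, onset date, duration, frequency, severity, seriousness, treatment, outcome and relationship. Limb, side and muscle are not among them. Appendix 1 gives the injection-site assessment its own row, apart from adverse events, and section 14 sends all study-procedure data to CRFs.

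**Analysis.** Section 6.2.1 defines the population ("Any patient who receives VM202 will be included in the safety analysis population") and plans descriptive summaries of AEs, SAEs and AEs leading to treatment discontinuation. The synopsis says that AEs "will be described according to severity and to their relationship with the study drug and injection procedure". Neither gives a breakdown by muscle, limb region or side.

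**The concern.** If the site wording means what it appears to mean, the stated primary endpoint has no matching analysis. A sponsor could follow sections 4.2.11, 5.2 and 6.2.1 to the letter and finish with pooled AE counts and nothing reportable by site. The report might then be unable to describe local tolerability separately for hand, forearm, upper arm, thigh, calf and shin. Location is easy to code at the visit. Reconstructing it from free text later may leave gaps.

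**Working it through.** **1. Do the listed items or the dates give location?**

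- Section 4.2.11 schedules nine site assessments per patient: Day 0 post-injection (1), Days 7, 14 and 21 pre- and post-injection (6), Day 30 and Day 60 (2). It attaches no location item to any of them.
- None of the nine AE items in section 5.2 is a location item. The relationship item separates drug, procedure and disease, not site. The description item could hold location as free text, but this is not required.
- Arms and legs are injected at separate visits a week apart (section 3.2). Up to the Day 7 injection only one limb pair has been exposed, so onset date identifies the limb pair. After that both have been exposed, and the date is only a clue.
- Even when the limb pair is known, 3 regions × 2 sides = 6 locations remain. By muscle and side it is 7 × 2 = 14 for the arms and 3 × 2 = 6 for the legs. The date never gives side or muscle.

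**2. Reproducing the plan's exposure figures (Tables 1 and 2)**

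Each injection is 0.5 mL × 0.5 mg/mL = 0.25 mg.

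- Arm visit: (2+2+8+8+2+2+2) × 2 sides = 52 injections; 52 × 0.25 = 13 mg.
- Leg visit: (20+12+6) × 2 sides = 76 injections; 76 × 0.25 = 19 mg.
- Total over two visits each: 2 × (52+76) = 256 injections; 2 × (13+19) = 64 mg. Both match the tables.

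**3. Planned injections per patient by region (both sides, all visits)**

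| Region | Sum | Injections |
|---|---|---|
| Hand | 8+8 | 16 |
| Forearm | 8+8+8 | 24 |
| Upper arm | 32+32 | 64 |
| Arms, total | | 104 |
| Thigh | | 80 |
| Calf | | 48 |
| Shin | | 24 |
| Legs, total | | 152 |

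If every injection carried the same chance of a reaction (an assumption used only to show the effect of exposure), expected raw counts would be 152/104 = 1.46 times higher in legs than in arms, and 80/16 = 5 times higher in thigh than in hand, with no true site difference. A regional table therefore needs injections given as a denominator as well as patients.

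**4. Patient denominator**

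Section 3.5.2 allows additional subjects when someone discontinues before the Day 90 visit, and section 6.2.1 keeps everyone who was treated. As an illustration, suppose one leg-first patient stops before the Day 7 visit and is replaced by a patient who completes. Then 19 are treated, 19 have been injected in the legs and 18 in the arms. The denominator for a region should be the patients injected there, not a fixed 18.

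**5. What the table could show**

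With no reaction in a region, the upper end of the exact two-sided 95% interval is 1 − 0.025^(1/18) = 18.5% for n = 18, and 1 − 0.025^(1/19) = 17.6% for n = 19. That is enough to describe a region and too little to compare regions.

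Steps 3 to 5 show how a by-site table should be built. They do not measure harm from its absence, and no planned result changes.

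**The case against.** The strongest answer is that no by-site result was ever meant. The site wording can simply say that patients are injected in many places. The design has one arm, every patient is to receive the same number of injections per muscle group, and no site contrast is built in. Several statements of the aim leave the wording out, and Appendix 4 uses almost the same words for separate spots within one target muscle. This stands as real ambiguity. It does not settle the matter, because the wording appears in the objective and in both statements of the primary endpoint.

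A reader might go further and infer that location is not collected. The documents do not support that. The injection-site assessment is a separate scheduled procedure whose CRF page was not supplied, the AE description is a natural place to write where a reaction occurred, and parts of section 3.2 and Appendix 4 are redacted. What can be said is that the readable protocol does not require it.

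A reader might also infer that serious local harm would go unnoticed. It would not: section 3.2 suspends the study pending DSMB review for injection-site tissue necrosis attributed to VM202, and section 5.4.1 requires complete information on every SAE.

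Finally, muscle circumference and MRC strength are recorded by side and body part, but this proves little about reaction location, since those measurements cannot be taken without naming the part.

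**Conclusion.** The point holds in a limited form. The objective and primary endpoint can be read as asking for safety and tolerability by injection site. The planned safety summaries are not by site, and the listed AE items do not require limb region or side. Location may be captured on the CRF, but the protocol does not ensure it, and even complete location data would have no planned table. The gap mainly concerns non-serious local reactions.

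This is a cheap improvement to consider. It does not show that the primary endpoint is unanswerable or that collection has failed. It rests on the by-site reading being at least partly intended and on the readable text alone. A CRF that already codes region and side would leave only the table to add.

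**What to change.** - **Section 4.2.11:** require limb region (hand, forearm, upper arm, thigh, calf, shin) and side for every injection-site reaction.
- **Section 6.2.1:** add one descriptive table by region giving (a) patients with at least one reaction out of patients injected in that region, and (b) reactions per injection given. State that cells will be sparse and that limb is confounded with visit dose (13 mg arms, 19 mg legs), so the table describes and does not compare.

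A sentence saying what the site wording means, and bringing the opening of section 6 into line with sections 3.1 and 6.2, would be a useful addition. Alone it would clear up the wording but add no information on local tolerability.

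**Cost:** one extra code per reaction and one table. No added patients, visits or hypothesis tests.

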### **6.2.1. SAFETY**

Any patient who receives VM202 will be included in the safety analysis population. Adverse events, serious adverse events, and adverse events leading to treatment discontinuation will be summarized using descriptive statistics. Categorical variables will be summarized by the number and percentage of patients in each category. Continuous variables will be summarized using n, mean, SD, median, minimum, and maximum values. No statistical testing will be performed.

### **6.2.2. PHARMACOKINETICS & PHARMACODYNAMICS**

HGF serum levels will be determined immediately pre-treatment on Day 0, immediately pre-treatment on Day 7, immediately pre-treatment on Day 14, immediately pre-treatment on Day 21, on Day 30, Day 60, and Day 90. The number of copies of VM202 in whole blood will be determined at Day 0 (pre-injection, and 2 hours [ $\pm$  1 hour] post last injection), at Day 7 (pre-injection, and 2 hours [ $\pm$  1 hour] post last injection), at Day 14 (pre-injection, and 2 hours [ $\pm$  1 hour] post last injection), at Day 21 (pre-injection, and 2 hours [ $\pm$  1 hour] post last injection), on Day 30, Day 60, and Day 90.

### **6.2.3. EFFICACY**

This is a phase I/II study, not powered to detect differences in efficacy measures. However, descriptive statistics of clinically meaningful endpoints will be tabulated. The potential of VM202 to reduce neurodegeneration and muscle wasting will be characterized using the ALSFRS-R, muscle strength (MRC scale), muscle circumference measurements and dynamometry. FVC will also be tracked and trended. Survival will also be recorded.

---

## **7. ACCESS TO STUDY DOCUMENTS AND STUDY MONITORING**

The Sponsor has designated MedTech Consultants to monitor the progress of this study. The clinical monitor, as a representative of the Sponsor, has the obligation to follow this study closely. In addition to conducting a site visit prior to initiation of enrollment, the clinical monitor will visit the study facilities regularly, and utilize telephone and written communications on an ongoing basis to maintain current knowledge of the study.

During periodic visits to the study site, the monitor will review the source documents used in the preparation of the CRFs to verify the accuracy and completeness of the information contained in those reports in preparation for retrieval. All source documents must contain all information required by the CRF. All data generated during this study and the source documents from which they originated are subject to inspection by the Sponsor or its representatives, the FDA and other regulatory agencies.

Upon completion of the study, the clinical monitor will conduct a final visit (close-out) to the site. The objectives of this visit are to ascertain that all regulatory records and reports

---

are complete, verify that study drug and other supplies have been accounted for and ensure that the Investigator is aware of his/her responsibilities post-study.

---

## **8. QUALITY CONTROL AND ASSURANCE**

---

The Sponsor employees and/or their contracted representatives utilize Standard Operating Procedures (SOP) designed to ensure that research procedures and documentation are consistently conducted/prepared to the highest quality standards. These SOPs also require compliance with Health Authority regulations and Good Clinical Practice guidance.

A Quality Assurance audit may be conducted by the Sponsor or its designee at any time during or after completion of a study. The Investigator will be given adequate notice if he/she is selected for an audit. The audit will include, but is not limited to, a review of all informed consent forms, a review of CRFs, associated source documents and medical records, a review of regulatory documentation, an assessment of study conduct and protocol compliance, and a review of the investigational drug accountability. At the conclusion of an audit, the auditor will conduct a brief meeting with the Investigator to review the findings of the audit.

---

## **9. INSTITUTIONAL REVIEW BOARD (IRB)**

---

Prior to the initiation of the study, the protocol, the informed consent form and Investigator's brochure will be submitted to the IRB for approval. By signing the "Statement of Investigator" form (form FDA 1572), the Investigator is assuring that an IRB which complies with the requirements set forth in 21 CFR Part 56 will be responsible for the initial and continuing review of the proposed clinical study. A copy of the IRB approval letter for the protocol, the informed consent, and the protocol signature page must be submitted to the Sponsor or its designee, prior to release of investigational supplies to the study site. The approval letter must refer to the specific protocol and the informed consent form. The study site must maintain an accurate and complete record of all reports, documents and other submissions made to the IRB concerning this protocol. A list of the IRB members, their titles or occupations, and their institutional affiliation, or an IRB assurance number must be provided to the Sponsor or its designee prior to release of study supplies.

FDA/relevant health authority regulations require that all advertisements for subject recruitment be approved by an IRB prior to implementation. The complete text and format must be submitted to the Sponsor or its designee for approval prior to IRB submission.

The Investigator is responsible for notifying the IRB of any SAEs as required by the IRB. A copy of the notification must be forwarded to the Sponsor or its designee.

Status reports must be submitted to the IRB at least once a year (or more frequently as required by the IRB) and the IRB must be notified of completion or termination of the

---

study. A final report must be provided to the IRB and the Sponsor within 3 months of study completion or termination. This report should include: any deviations from the protocol, the number of participants evaluated, the number of participants who withdrew or were withdrawn and the reasons for withdrawal, any significant adverse events and the Investigator's summation of the study.

---

#### **10. INSTITUTIONAL BIOSAFETY COMMITTEE (IBC)**

---

The site at which this trial is being conducted will ensure that an Institutional Biosafety Committee (IBC) is in place. The IBC will ensure that the site conforms to the requirements set forth in the Section IV-B-2 of the National Institutes of Health (NIH) Guidelines for Research Involving Recombinant DNA Molecules, promulgated by the National Institutes of Health/Office of Biotechnology Activities (NIH/OBA).

The Investigator will be responsible for petitioning the IBC and obtaining approval prior to enrolling any subject in the study. The Investigator will also be required to obtain and follow all biohazard safety guidelines promulgated by the IBC, and to report all findings as required to the IBC and to NIH/OBA.

If a potential clinical site does not receive any NIH funding (either directly or indirectly) and does not have an institutional IBC, they can participate in the study if they issue a certification statement to that effect. The certification statement will be submitted to the OBA.

---

